4.5.1.1 Risk Assessment Curves for Holding Rules Cutoff Definition

Figure 2 Blinded Review: Safety Holding Rules 1a, 1b, 1c, 1d.1 and 2c After 10, 21, 40 and 105 Participants

[figure not shown]

Figure 2 illustrates the following:

- With 10 participants, each holding rule 1a-d.1, and 2c has more than 90% chance of not being met for study intervention administration with a true incidence rate below 1% and has more than 65% chance of being met for study intervention administration with a true incidence rate above 10%.
- With 21 participants, each holding rule 1a-d.1 has more than 80% chance of not being met for study intervention administration with a true incidence rate below 1% and has more than 65% chance of being met for study intervention administration with a true incidence rate above 4.8%.
- With 40 participants, each holding rule 1a-d.1, and 2c has more than 70% chance of not being met for study intervention administration with a true incidence rate below 1% and has more than 65% chance of being met for study intervention administration with a true incidence rate above 2.5%.
- With 105 participants, each holding rule 1a-d.1 has more than 90% chance of not being met for study intervention administration with a true incidence rate below 1% and has more than 88% chance of being met for study intervention administration with a true incidence rate above 2.0%.

Figure 3 Unblinded Review: Safety Holding Rules 1d.2 After 4, 9, 16 and 45 Participants

[figure not shown]

Figure 3 illustrates the following:

- With 4 participants in administration cohort, holding rule 1d.2 has more than 90% chance of not being met for study intervention administration with a true incidence rate below 2.5% and has more than 68% chance of being met with a true incidence rate above 25%.
- With 9 participants in administration cohort, holding rule 1d.2 has more than 90% chance of not being met for study intervention administration with a true incidence rate below 6% and has more than 63% chance of being met for study intervention administration with a true incidence rate above 22.2%.
- With 16 participants in administration cohort, holding rule 1d.2 has more than 85% chance of not being met for study intervention administration with a true incidence rate below 1% and has more than 65% chance of being met with a true incidence rate above 6.2%.
- With 45 participants in administration cohort, holding rule 1d.2 has more than 80% chance of not being met for study intervention administration with a true incidence rate below 2% and has more than 60% chance of being met with a true incidence rate above 4.4%.

Figure 4 Unblinded Review: Safety Holding Rules 2a and 2b After 4 and 16 Participants

[figure not shown]

Figure 4 illustrates the following:

- With 4 participants in administration cohort, each holding rule 2a and 2b has more than 90% chance of not being met for study intervention administration with a true incidence rate below 14% and has more than 69% chance of being met for study intervention administration with a true incidence rate above 50%.
- With 16 participants in administration cohort, each holding rule 2a and 2b has more than 90% chance of not being met for study intervention administration with a true incidence rate below 3% and has more than 61% chance of being met for study intervention administration with a true incidence rate above 12.5%.

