An additional 20 mL for assay development will be taken in Stage 1 on Day 85 from the participants who have given specific consent.

§ Out-of-window vaccination is not allowed.

¹ For literate participants in Europe/Africa only

² For illiterate participants in Africa only

³ The pre 2nd and 3rd vaccination screening in Malawi could take more than a day, necessitating additional site visits but not more than 72 hours prior to the actual receipt of the vaccination.

⁴ For illiterate participants, pDiary cards will be completed by the site field worker.

⁵ For illiterate participants, pDiary cards can be returned by the field worker at the end of the 7 days after administration.

⁶ For Malawi (Stage 2) only, subjects who test positive for malaria at Screening will be temporarily excluded (even if asymptomatic) and enrollment/first vaccination delayed until a negative malaria highly sensitive RDT is available. Treatment will also be provided for such prospective participants at the Investigator's discretion according to local guideline. For subsequent vaccinations, malaria RDT testing will only be performed if participants have symptoms suggestive of malaria.

⁷ Home visit for safety follow-up will take place only on Day 2.

Table 2 Intervals Between Study Visits

Interval	Planned visit interval	Allowed interval range
Screening (Day -28) → Visit 1 (Day 1)	Up to 28 days*	Up to 28 days*
Visit 1 (Day 1) → Visit 2 (Day 8)	7 days	7-10 days
Visit 1 (Day 1) → Reminder phone call 1 (Day 4)	3 days	1-3 days
Visit 1 (Day 1) → Visit 3 (Day 29)	28 days	28-33 [#] days**
Visit 1 (Day 1) → Visit 4 (Day 57)	56 days	52-62 days**
Visit 4 (Day 57) → Visit 5 (Day 64)	7 days	7-10 days
Visit 4 (Day 57) → Reminder phone call 2 (Day 60)	3 days	1-3 days
Visit 4 (Day 57) → Visit 6 (Day 85)	28 days	28-33 [#] days**
Visit 4 (Day 57) → Visit 7 (Day 169)	112 days	110-126 days**
Visit 4 (Day 57) → Visit 7 (Day 169)	112 days	110-140 ^{\$} days**
Visit 7 (Day 169) → Visit 8 (Day 176)	7 days	7-10 days
Visit 7 (Day 169) → Reminder phone call 3 (Day 172)	3 days	1-3 days
Visit 7 (Day 169) → Visit 9 (Day 197)	28 days	28-33 [#] days**
Visit 7 (Day 169) → Visit 10 (Day 337)	168 days	154-182 days

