- GSK will further evaluate the case with the iSRC and GSK Global Safety Board and will take the decision to stop or to restart the study intervention administration. GVGH project physician will inform the IQVIA project lead of the decision and the rationale for the decision and all site staff will be informed about that final decision by IQVIA project lead.

Table 5 Study Holding Rules

Events	Number or % of participants needed to pause administration of study intervention	
	Stage 1 Step 1 and Step 2	Stage 2
1a Death or any life-threatening SAE regardless of causality	≥1	≥1
1b Any non-life-threatening SAE that cannot be reasonably attributed to another cause other than study intervention administration	≥1	≥1
1c Any withdrawal from the study (by Investigator or participant request) following a Grade 3 AE that cannot be reasonably attributed to another cause other than study intervention administration	≥1	≥1
1d.1 Any administration site or general solicited event leading to hospitalization, OR Necrosis at the injection site, each within the 7-day (Days 1 to 7) post-administration period	≥1	≥1
1d.2 Fever >40°C (104°F) within the 7-day (Days 1 to 7) post-administration period	≥1	≥2
2a Any Grade 3 solicited administration site event (lasting 48 h or more) in an investigational group, within the 7-day (Days 1 to 7) post-administration period	≥2	NA
2b Any Grade 3 solicited general AE (lasting 48 h or more) in an investigational group, within the 7-day (Days 1 to 7) post-administration period	≥2	NA
2c Any Grade 3 unsolicited AE in an investigational group, that can be reasonably attributed to the study intervention administration, within the 7-day (Days 1 to 7) post-administration period or Any Grade 3 abnormality in prespecified hematological or biochemical laboratory parameters in an investigational group within the 7-day (Days 1 to 7) post-administration period	≥1	NA

Abbreviations: AE = adverse event; h = hours; SAE = serious adverse event; NA = not applicable

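### The 105-participant bullet for the one-event holding rules is wrong: at a 1% event rate the chance of no hold is 34.8%, not above 90%

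*Protocol*

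**What the plan says.** Table 5 and Section 4.5.1 of the Protocol set rules 1a to 1d.1 at one or more participants with an event, in both stages. Rule 1d.2 (fever above 40°C) has a threshold of one in Stage 1 and two in Stage 2.

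Section 4.5.1.1 then states how the rules behave. The statements at issue are:

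- **105 participants:** "With 105 participants, each holding rule 1a-d.1 has more than 90% chance of not being met for study intervention administration" at a true rate below 1%, with a chance above 88% of being met at a rate above 2.0%.
- **40 participants:** "With 40 participants, each holding rule 1a-d.1, and 2c has more than 70% chance of not being met" below 1%, and above 65% met above 2.5%.
- **21 participants:** "With 21 participants, each holding rule 1a-d.1 has more than 80% chance of not being met" below 1%, and above 65% met above 4.8%.
- **16 participants, rule 1d.2:** "has more than 65% chance of being met with a true incidence rate above 6.2"%.
- **45 participants, rule 1d.2:** "With 45 participants in administration cohort, holding rule 1d.2 has more than 80% chance of not being met" below 2%, and above 60% met above 4.4%.

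On rule 2c, which applies in Stage 1 only, Table 5 counts "Any Grade 3 abnormality in prespecified hematological or biochemical laboratory parameters in an investigational group within the 7-day (Days 1 to 7) post-administration period". Section 4.5.1 says that rules 1 and 2c trigger a hold whatever the timing of the event relative to dosing. Tables 1 and 3 schedule the 7-day safety bloods on Days 8, 64 and 176, and Table 2 allows those visits 7 to 10 days after the dose.

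**The concern.** For a one-event rule at a fixed event rate, the chance of seeing no event must fall as more people are exposed. At the same 1% rate the text gives 90% for 10 participants, 80% for 21 and 70% for 40, then returns to 90% for 105. The last figure cannot be right if the threshold is one event.

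This section presents the cutoffs' operating characteristics. A reader judging how likely Stage 2 is to be interrupted would conclude that a hold under any one of these rules is unlikely at a 1% rate, when it is more likely than not. Pauses have a cost here: the footnote to Table 1 says "Out-of-window vaccination is not allowed", so a pause that outlasts a dosing window loses doses.

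The rule 2c point is separate and smaller. If the window is read literally, no scheduled post-dose sample can trigger the laboratory part of the rule. An investigator with a Grade 3 value from the Day 8 sample gets one answer from Table 5 and another from Section 4.5.1.

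**Working it through.** **Inputs.** Cohort sizes, rates and claimed probabilities come from Section 4.5.1.1; thresholds come from Table 5 and Section 4.5.1.

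**Formula.** Exact binomial, n independent participants, per-participant rate p.

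- Threshold 1: P(not met) = (1 − p)^n.
- Threshold 2: P(not met) = (1 − p)^n + n·p·(1 − p)^(n−1).
- P(met) = 1 − P(not met).

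**Reproducing the plan's own figures.**

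- n = 10: 0.99^10 = 90.4% not met (stated above 90%); 1 − 0.90^10 = 65.1% met (stated above 65%).
- n = 21: 0.99^21 = 81.0% not met (stated above 80%).
- n = 105: 1 − 0.98^105 = 88.0% met (stated above 88%).

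So this is evidently the plan's method.

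**The 105 bullet, first half.** 0.99^105 = 34.8% not met, and 65.2% met. The shortfall from 90% is about 55 points.

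**Does another threshold rescue it?**

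| Threshold, n = 105 | Not met at 1% (stated above 90%) | Met at 2% (stated above 88%) |
|---|---|---|
| 1 | 34.8% | 88.0% |
| 2 | 71.7% | 62.3% |
| 3 | 91.1% | 35.1% |

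No row satisfies both halves. Reading the rate strictly as below 1% does not help either: solving (1 − p)^105 = 0.90 gives p = 0.10%, so the claim fails for rates from about 0.1% up to 1%. At exactly 0.1%, 0.999^105 = 90.03%.

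**Sequence at 1%, threshold 1.** 90.4% (n = 10), 81.0% (n = 21), 66.9% (n = 40), 34.8% (n = 105).

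**Smaller misses.**

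| Bullet | Calculation | Result | Stated |
|---|---|---|---|
| n = 40, not met at 1% | 0.99^40 | 66.9% | above 70% |
| n = 40, met at 2.5% | 1 − 0.975^40 | 63.7% | above 65% |
| n = 45, threshold 2, not met at 2% | 0.98^45 + 45 × 0.02 × 0.98^44 = 0.403 + 0.370 | 77.3% | above 80% |
| n = 21, met at 4.8% | 1 − 0.952^21 | 64.4% | above 65% |
| n = 16, threshold 1, met at 6.2% | 1 − 0.938^16 | 64.1% (64.4% at 1/16) | above 65% |

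The 60% figure for n = 45 is 60.01% at 2/45 (59.5% at the printed 4.4%) and is accepted. Two further figures fall short by rounding only: 62.7% against 63% (n = 9) and 68.75% against 69% (n = 4, rules 2a and 2b).

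**Rule 2c.** With dosing on Day 1, a draw 7 to 10 days later falls on Day 8 to Day 11 of that dose's count. The only other scheduled post-dose draw is at 28 days. None of the scheduled post-dose samples falls in Days 1 to 7.

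**The case against.** The strongest reply is that nothing operative rests on these sentences. The thresholds in Table 5, the investigator's continuous assessment and the committee review that decides on restart are all unaffected, and the rules are stricter than described, so participants are no less protected. That is correct, and it limits the severity. It does not make the figure right.

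The planning cost can also be called speculative. The protocol does not assume a 1% rate for these events, gives no hold duration, and allows 110 to 140 days between the second and third doses in Stage 2 (52 to 62 days between the first and second). This stands: the 65% is conditional on a 1% rate, and doses lost cannot be estimated from the documents.

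On the smaller misses, the shortfalls for 21 and 16 participants are under one point and close to rounding. They would not merit an amendment alone. The not-met figures for 40 and 45 participants miss by 3.1 and 2.7 points, which is more than rounding.

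On rule 2c, the timing sentence in Section 4.5.1 can be read as already covering the Day 8 sample, and investigators may order extra tests (Section 8.2.2). Safety committee review #1 receives Step 1's 7-day laboratory listings, review #2 covers Step 1 to Day 64, and review #3 covers the full-dose step. Blinded monitoring covers all of Stage 1 to 7 days after each dose (Table 15), and the latest laboratory results are checked before doses 2 and 3 (Section 5.5). The amendment summary shows Stage 1 already under way, so rewording may have limited forward effect. These points reduce the risk, but they leave two conflicting instructions about an immediate suspension.

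**Conclusion.** The concern holds. With a one-event threshold, 105 participants and a 1% rate, each of rules 1a to 1d.1 has a 34.8% chance of not being met. The chance of a Stage 2 hold is therefore 65.2% per rule, where the text implies under 10%. The likeliest cause is 0.1% printed as 1%; this is an inference, because the figure is not visible and only the bullet text could be checked.

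The lesser errors are a hold chance of 33.1% against an implied under 30% (40 participants, 1% rate) and 22.7% against under 20% (45 participants, rule 1d.2, 2% rate). Three met figures of about 64% are stated as above 65%.

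The calculations assume independent participants, a common per-participant rate and complete data on the stated number. The rule 2c conflict is a wording defect confined to Stage 1. Overall this should be corrected, but it does not call the rules themselves into question.

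**What to change.** In Section 4.5.1.1:

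- **105 participants:** state about a 35% chance of not being met at 1%, or 90% at 0.1%; keep 88% met at 2.0%.
- **40 participants:** about 67% not met at 1% and about 64% met at 2.5%.
- **45 participants (rule 1d.2):** about 77% not met at 2%; keep the 60% figure.
- **21 and 16 participants:** about 64% met, changed in the same edit.

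Check the plotted curves against the corrected bullets.

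In Table 5, rule 2c (Stage 1): extend the laboratory window to include the scheduled 7-day post-dose visit (Days 8, 64 and 176, allowed 7 to 10 days after dosing), and align the timing sentence in Section 4.5.1 with it.

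The cost is a protocol text correction. No threshold, sample size or analysis changes. The visible consequence is that the stated chance of a Stage 2 hold at a 1% rate rises from under 10% to about 65% per rule.

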4.5 Study Holding Criteria

4.5.1 Study Holding Rules

Holding rules will be introduced to ensure a well-controlled exposure to the investigational candidate vaccine and to prevent participants from being exposed to any unnecessary safety risks in this FIH study. The holding rules will point attention to safety signals and indicate requirements for formal committee reviews that will decide whether additional participants can be exposed to the study intervention if particular criteria are met. Study holding rules are defined in [Table 5](#).

Holding rule 1 and 2c (threshold ≥ 1) will be assessed by the Investigator on a continuous basis irrespective of the number of enrolled participants and meeting any of these holding rules will trigger a hold of study intervention administration irrespective of number of enrolled participants and/or timing of the event relative to study intervention administration. Holding rule 2 (2a-b) and 1d.2 in Stage 2 (threshold ≥ 2) will be assessed during the safety evaluations on blinded or unblinded data.

These holding rules have been written under the assumption that the safety data from all participants will be available. If the data from some participants are not available (eg, in case a participant is lost to follow-up), then the holding rules will be assessed on a pro-rata basis.

If the Investigator becomes aware of a holding rule being met, he/she must suspend administration of the study intervention and inform the Sponsor's delegate immediately (holding rules 1a-d and 2c).

However, for the other holding rules (1d.2 in Stage 2, 2a and 2b) which have a threshold ≥ 2 , the Investigator will inform the Sponsor's delegate immediately, without suspending the administration of the study intervention.

The Sponsor's delegate will inform the Investigator if holding rules 1d.2 in Stage 2 and 2a-b are met.

The following communication sequence must be followed:

- The concerned site staff has to put study intervention administration on hold.
- The concerned site staff must immediately inform IQVIA CRA and Medical Monitor (contact details will be provided in a separate document) via email and phone communication who will in-turn inform the GVGH Study Responsible Project Physician.
- All informed site staff will confirm to their local contact that action has been taken providing appropriate documentation to GVGH through the IQVIA CRA and Medical Monitor.

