6.3.3 Blinding and Unblinding

Data will be collected in an observer-blind manner. By observer-blind, it is meant that during the course of the study, the vaccine recipient and those responsible for the evaluation of any study endpoint (eg, safety and reactogenicity) will all be unaware of which study intervention was administered.

To do so, vaccine preparation and administration will be done by authorized medical personnel who will not participate in any of the study clinical evaluations.

The laboratory in charge of the laboratory testing will be blinded to the treatment, and codes will be used to link the participant and study (without any link to the treatment attributed to the participant) to each sample.

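### Protocol 4.5.1.1 misstates three chances that a holding rule is not met; with 105 participants and a 1% rate the figure is 34.8%, not above 90%

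*Protocol*

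**What the plan says.** Protocol Table 5 sets the number of participants with an event that pauses dosing. It is one for rules 1a, 1b, 1c and 1d.1 in both stages, and one for rule 2c in Stage 1. For rule 1d.2 it is one in Stage 1 and two in Stage 2. For rules 2a and 2b, which apply in Stage 1 only, it is two. Section 4.5.1 says that the threshold-one rules "will be assessed by the Investigator on a continuous basis irrespective of the number of enrolled participants".

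Section 4.5.1.1 then gives, for each cohort size, the chance that a rule is not met at a low true rate and the chance that it is met at a higher one. Three of the *not met* statements matter here:

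- Figure 2: "With 105 participants, each holding rule 1a-d.1 has more than 90% chance of not being met", for a rate below 1%.
- Figure 2: "With 40 participants, each holding rule 1a-d.1, and 2c has more than 70% chance of not being met", for a rate below 1%.
- Figure 3: "With 45 participants in administration cohort, holding rule 1d.2 has more than 80% chance of not being met", for a rate below 2%.

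**The concern.** For a rule that fires at the first event, the chance of not firing must fall as more people are dosed at the same rate. The Figure 2 bullets, all for a rate below 1%, give more than 90%, 80% and 70% at n = 10, 21 and 40, and then return to more than 90% at n = 105. That cannot be right for a fixed threshold of one.

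The bullets state how the safety rules of a first-in-human study are expected to behave. Someone relying on the n=105 bullet would plan for less than a 10% chance that a given rule pauses dosing in Stage 2 when the true rate is 1%. A pause leads to a committee evaluation and a decision to stop or restart, in a study whose schedule does not allow vaccination outside the visit window. How often to expect one is therefore of practical interest.

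**Working it through.** **Inputs.** Thresholds r come from Table 5. Cohort sizes n, rates p and stated bounds come from the bullets in Section 4.5.1.1. Participants are taken as independent with a common rate, and each bound is evaluated at the edge of its stated range, where it is tightest.

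**Formulas.**

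- r = 1: P(not met) = (1 − p)^n
- r = 2: P(not met) = (1 − p)^n + n·p·(1 − p)^(n−1)
- P(met) = 1 − P(not met)

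**Reproducing the plan's figures first.** Figure 2 with n=10 gives 0.99^10 = 90.4% not met (stated above 90%) and 1 − 0.90^10 = 65.1% met (stated above 65%). The second half of the n=105 bullet also reproduces: 1 − 0.98^105 = 88.0% (stated above 88% at 2.0%). The method and thresholds are therefore those of the protocol.

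**All ten bullets.**

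| Figure | n | r | Not met: rate, stated | Computed | Met: rate, stated | Computed |
|---|---|---|---|---|---|---|
| 2 | 10 | 1 | 1%, >90% | 90.4% | 10%, >65% | 65.1% |
| 2 | 21 | 1 | 1%, >80% | 81.0% | 4.8%, >65% | 64.4% |
| 2 | 40 | 1 | 1%, >70% | **66.9%** | 2.5%, >65% | 63.7% |
| 2 | 105 | 1 | 1%, >90% | **34.8%** | 2.0%, >88% | 88.0% |
| 3 | 4 | 1 | 2.5%, >90% | 90.4% | 25%, >68% | 68.4% |
| 3 | 9 | 2 | 6%, >90% | 90.2% | 22.2%, >63% | 62.7% |
| 3 | 16 | 1 | 1%, >85% | 85.1% | 6.2%, >65% | 64.1% |
| 3 | 45 | 2 | 2%, >80% | **77.3%** | 4.4%, >60% | 59.5% |
| 4 | 4 | 2 | 14%, >90% | 90.3% | 50%, >69% | 68.75% |
| 4 | 16 | 2 | 3%, >90% | 91.8% | 12.5%, >61% | 61.2% |

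**The three failures in full.**

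- n=105: 0.99^105 = 0.3481, so the chance of a pause is 1 − 0.3481 = 65.2% for each rule. The shortfall against 90% is about 55 points.
- n=40: 0.99^40 = 0.6690, a shortfall of 3.1 points.
- n=45: 0.98^45 + 45 × 0.02 × 0.98^44 = 0.7729, a shortfall of 2.7 points.

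**Rate up to which each bound does hold.** About 0.10% for n=105, 0.89% for n=40 and 1.84% for n=45. The n=105 statement is thus false over roughly nine-tenths of the range it claims; the other two are false only near the top of theirs.

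**Does another threshold explain them?** No threshold of 1, 2 or 3 fits both halves of any of the three bullets.

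- n=105: r = 2 gives 71.7% not met and 62.3% met; r = 3 gives 91.1% not met but only 35.1% met at 2%.
- n=40: r = 2 gives 93.9% not met but 26.4% met at 2.5%.
- n=45: r = 1 gives 40.3% not met; r = 3 gives 93.9% not met but 31.8% met at 4.4%.

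**The case against.** **The n=105 error may be one digit.** At a rate of 0.1%, 0.999^105 = 90.0%, which matches the stated bound, and the other half of the bullet is correct. This is a plausible explanation, but the documents do not say it. The sentence as printed is wrong either way.

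**Only the bullets can be checked.** Figures 2 to 4 are not shown, and the curves themselves may be right. This stands: the point concerns the text.

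**Two of the three misses are small.** This also stands. n=40 and n=45 are about 3 points out and should not be put beside n=105. For rule 2c alone, which Table 5 limits to an investigational group, 32 vaccinees would give 0.99^32 = 72.5% and satisfy the n=40 bound. But the bullet is written for 40 participants and covers rules 1a to 1d.1, which have no such limit.

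**Stronger readings the documents do not support.**

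- *That the thresholds are wrong or participants less protected.* One event is the lowest possible count, so a corrected percentage could not make rules 1a to 1d.1 stricter. No sentence says that a threshold was chosen to reach a given chance; only the section heading links the curves to the cutoffs.
- *That a 65.2% chance of a pause is a false-alarm rate.* The protocol nowhere calls a 1% rate acceptable. For deaths or related serious events in healthy volunteers, a pause is not obviously false.
- *That the Stage 1 figures for rule 1d.2 are wrong because they are per group.* Table 5 words the event as "Fever >40°C (104°F) within the 7-day (Days 1 to 7) post-administration period", with no group limit, and evaluators are blinded ("those responsible for the evaluation of any study endpoint (eg, safety and reactogenicity) will all be unaware of which study intervention was administered"), so a single case in any arm stops dosing. But "With 4 participants in administration cohort, holding rule 1d.2 has more than 90% chance of not being met" and "With 16 participants in administration cohort, holding rule 1d.2 has more than 85% chance of not being met" are both correct for one group (90.4% and 85.1%). The n=10 and n=40 curves of Figure 2 apply numerically to any threshold-one rule, so no extra figure is needed.
- *That nearly half of the 20 bounds are in error.* Besides the three above, six *met* bounds fall short as written, by at most 1.3 points. That is rounding: n=45 at the unrounded rate 2/45 gives 60.0% and meets its bound.

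**Conclusion.** The point holds for three *not met* statements, of which one is a gross error. With 105 participants and a 1% rate, each of rules 1a to 1d.1 has a 34.8% chance of not being met, against a stated figure above 90%. The n=40 and n=45 statements are small misses, and all three understate how often dosing would pause. The result rests on the Table 5 thresholds, independent participants and a common rate; the halves of the bullets that do reproduce support that reading. The consequence is a misstated property of the safety rules in the protocol text. A met rule leads to review and possible restart, so nothing in the conduct of the rules is affected.

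**What to change.** In Protocol Section 4.5.1.1:

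1. n=105: state about 35% at a rate of 1%, or change the rate to 0.1%, where the chance is 90.0%. Check which value the Figure 2 curve shows.
2. n=40: state about 67% (more than 66%) at 1%.
3. n=45, rule 1d.2: state about 77% at 2%.

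Optional while editing: lower the *met* bounds to more than 64% (n=21), 63% (n=40), 62% (n=9), 64% (n=16, Figure 3) and 68% (n=4, Figure 4). The n=45 *met* bound needs no change if its rate is written as 2/45.

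The cost is a few corrected numbers in one section. No threshold, endpoint, sample size or analysis changes.
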